Based on our analysis of likelihood of tumor growth or risk of metastasis, data will be analyzed every two years and appropriate revisions will be made to the surgical management guidelines, if indicated by data analysis.

As of February 1, 2011, 40 patients have been enrolled who have undergone all four imaging modalities (CT scan, MRI, 18F-DOPA, 18F-FDG). Only 11 of the 98 lesions (11%) were positive on 18F-DOPA as compared to CT scan. Based on this interim analysis, 18F-DOPA is not likely to be useful for detecting pancreatic neuroendocrine tumors in patients with VHL and as of amendment H this mode of imaging is no longer included in protocol evaluations.

As of April 15, 2014, 129 of 276 patients screened in the study had solid lesions. Of these 129 patients, 24 required operative intervention. FDG-PET detected metastatic disease in 3 patients which were not detected by CT, and found non-neoplastic disease in 4 patients. Hence, FDG-PET was able to find 29% of the surgical patients who either had metastasis not detected by CT or had non-neoplastic disease in which operation could be avoided. Using the method of Agresti-Coull (1998), the corresponding 90% confidence interval is (16.5%, 46%) with width 29.5%. Assume that the true proportion of diagnosis of metastatic as well as non-neoplastic disease by FDG-PET which is not detected by CT is 30%. To reduce the width of the 90% expected confidence interval to 20%, a total of 52 surgical patients are required. Correspondingly, approximately a total of 600 VHL patients need to be screened.

Power calculation for the comparison of tumor growth rates between two groups is based on comparing linear growth on the log-scale. Assuming that approximately 9% (54 patients) of screened VHL patients will present or develop pancreatic tumors which require operation over follow-up, we would have 95% power to detect a 1 standard deviation change in the growth rate between two groups of equal numbers (27 in each group) with a two-sided test the 0.05 significance level. This calculation is based on comparing individually estimated slopes (using multiple follow-up measurements on each subject) with a two-sample t-test. This calculation is only an approximation since power may be slightly reduced due to correlation across multiple individuals in the same family and may be increased due to multiple tumors followed on each patient.

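### The 600-patient target divides 52 by a single-date operation proportion that ignores follow-up time; at the stated accrual rate it is probably too high, but the direction is not certain.

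*Combined protocol and SAP*

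**What the plan says.** Section 8 reports the position at one date: "As of April 15, 2014, 129 of 276 patients screened in the study had solid lesions. Of these 129 patients, 24 required operative intervention". From the FDG-PET results in those 24 it estimates how often the scan shows metastasis that CT missed, or non-neoplastic disease. It then sets a precision goal: "To reduce the width of the 90% expected confidence interval to 20%, a total of 52 surgical patients are required". The next sentence gives the enrolment figure: "Correspondingly, approximately a total of 600 VHL patients need to be screened". No operation rate, person-time, follow-up length or counting date is given for that step.

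The following paragraph, on power for growth rates, takes about 9% of screened patients (54) as those who "will present or develop pancreatic tumors which require operation over follow-up".

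Other sections bear on the step:
- Section 3.2.2 provides yearly evaluation, with no stated end, for solid lesions that have not reached the size criteria.
- Section 3.3.2 lists enlargement on serial imaging among the reasons to consider surgery.
- Section 1.1.1 makes time to recommended surgery a primary objective.
- The Précis projects 25 patients a year for 15 years and a total of 600.

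**The concern.** Dividing 52 by 24/276 is right if each enrolled patient contributes the same expected number of operations at the second date as at the first. In a cohort that enrols continuously and stays under observation, this need not hold. At the 2014 date, 129 − 24 = 105 patients with solid lesions had not been operated on. Any of them who later come to surgery add to the 52 without new enrolment. So do patients with cystic disease who later develop a solid lesion. The 24 is a right-censored count, and its expected value depends on how long the 276 had been followed.

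The growth-rate paragraph has the same gap. It describes a proportion that accumulates over follow-up, but its 9% is close to the snapshot 8.7%.

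The 600 is the protocol's stated sample size. At 25 a year, the 600 − 276 = 324 patients still to come after the snapshot represent about 13 years of accrual.

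**Working it through.** **Inputs from the documents.** 276 screened, 129 with solid lesions and 24 operated on at 15 April 2014; 52 surgical patients required; target 600; 9% (54) in the growth-rate paragraph (all Section 8). Accrual of 25 a year for 15 years (Précis). Patients screened are treated as patients enrolled, as the Précis does with the 600.

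**Reproducing the plan.**
- Agresti-Coull 90% interval for 7/24: 16.5% to 46.0%, width 29.5%, as stated.
- At a true proportion of 30%, the expected width is 20.4% with 52 patients and 20.0% with 54, so 52 is accepted here.
- 24/276 = 8.70%, and 52/0.0870 = 598, the plan's 600.
- Growth-rate paragraph: 0.09 × 600 = 54.
- The older planning figures in Section 8 (26 operated of 300) also give 52/(26/300) = 600. They assume 17% with solid lesions and 50% of those operated on, whereas the 2014 data show 129/276 = 47% and 24/129 = 19%. That route has no follow-up time in it either.

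**Projection with follow-up time. Assumptions not in the documents:** uniform entry; 25 a year from the start, so 276 patients take 276/25 = 11.04 years; a share f of the 24 operations at entry; a constant hazard h for the rest; a constant loss hazard l.

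With p0 = f × 24/276, the probability of operation by u years after entry for those not operated on at entry is

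F(u) = h/(h + l) × [1 − exp(−(h + l)u)].

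Averaged over uniform entry during T years, P(T) = p0 + (1 − p0) × mean of F(u) for u from 0 to T.

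Solve h from P(11.04) = 24/276, then find T such that 25 × T × P(T) = 52, and N = 25T.

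Example with f = 0 and l = 0: P(T) = 1 − (1 − exp(−hT))/(hT), which gives h = 0.0167 per year. At T = 16.5 years, P = 0.126, so N is about 412 and 412 × 0.126 = 52. With no loss, N does not depend on the accrual rate as long as it is steady.

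| Operations at entry (f) | Yearly loss | N at which 52 are expected | Operations when 600 enrolled at 25 a year | Operations at year 15 if 600 enrolled by then |
|---|---|---|---|---|
| 0% | 0 | 412 | 106 | 51 |
| 0% | 10% | 452 | 78 | 48 |
| 25% | 0 | 430 | 94 | 51 |
| 25% | 10% | 471 | 72 | 49 |
| 50% | 0 | 456 | 81 | 52 |
| 50% | 10% | 497 | 66 | 50 |
| 75% | 0 | 500 | 67 | 52 |
| 75% | 10% | 535 | 59 | 51 |
| 100% | any | 598 | 52 | 52 |

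**How far the direction depends on accrual and counting date.**
- The last column has 276 patients entering over 11.04 years and 324 in the remaining 3.96, about 82 a year. In the first row the two groups contribute 40.2 + 10.5 = 50.7 operations.
- If the first 276 had instead taken 13 years, the same calculation (f = 0, no loss) gives about 36 operations at year 15.
- If follow-up in the 11-year case runs three more years after the last entry, 57 to 78 operations are expected.
- Taken literally, 25 × 15 = 375 patients, not 600. At year 15 these would yield about 34 to 43 operations, fewer than 52.

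**Sampling error.** The exact 95% interval for 24/276 is 5.65% to 12.66%. Then 52/0.1266 = 411 and 52/0.0565 = 920.

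**The case against.** The strongest reply is that the documents do not show 600 to be too many. The Précis gives 25 a year, 15 years and 600 patients, which cannot all hold. Keeping 25 a year with 600 means 24 years of accrual, and the surplus of operations depends on that choice. If 600 are reached by year 15 and counted then, average follow-up does not lengthen, and the simple division is about right whenever operations occur. This stands. A reader might infer that 600 is simply an overstatement, or that 598 is correct only if every operation happens at entry. Neither follows. Against that, the faster scenario needs about 82 patients a year, over three times the only rate the protocol states, and a count on the last enrolment day, which no section specifies.

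Second, the aim needs operations with an informative FDG-PET. Section 3.2.2 schedules PET at only two time points a year apart, and patients under 18 are not scanned. An operation years later may have no contemporaneous scan, so late operations may not all count towards the 52. This stands too, and it shapes the fix.

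Third, the protocol has other natural-history aims, and Section 1.2.1 intends to enrol as many patients as possible. So 600 may be wanted for reasons beyond the 52, and extra operations would only improve precision and power. That is fair, but Section 8 presents 600 as following from the 52.

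Fourth, Section 2.2 records that all patients were taken off study in the first half of 2009 and that those wishing to continue were re-registered. A smooth loss rate does not describe that. This limits the projection, and it is a further reason to use the actual dates.

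Finally, the Kaplan-Meier analysis serves a separate objective, so it does not in itself contradict the 600. It does show that operation is treated elsewhere as an event in time.

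**Conclusion.** The point holds as one of method. The division is done correctly, but the 600 and the 9% (54) rest on a single-date, right-censored proportion with no follow-up time, accrual pattern or counting date behind it.

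Under steady accrual of 25 a year with continued follow-up, 600 probably overstates what this aim needs: 52 operations at about 412 to 535 patients, and 59 to 106 operations by the time 600 are enrolled. This rests on uniform entry, a constant hazard, 0 to 75% of operations at entry, 0 to 10% yearly loss, and every operation counting towards the aim.

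The documents support nothing firmer. They give no entry dates, person-time or operation dates. Rapid later entry with an early count makes 600 about right or slightly low (48 to 52 operations), and the sampling range of 411 to 920 contains both 600 and the whole projected range.

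**What to change.** - State the target for this aim as 52 surgical patients with an FDG-PET usable for the endpoint, and define usable in terms of the interval between scan and operation.
- From the 276 patients' existing dates, estimate the cumulative incidence of operation by time since entry. Apply it to current and future patients, with a stated accrual rate and counting date, and restate the enrolment figure with its uncertainty. The off-study period in 2009 should be handled explicitly.
- Restate the 9% (54) in the growth-rate power paragraph from the same projection.
- Reconcile 25 a year for 15 years with 600 in the Précis.
- Update the projection at the two-yearly analysis that Section 8 already plans.
- If 600 is kept for other natural-history aims, say so and give that as the reason.

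The cost is one re-projection from dates the study should already hold, and an enrolment number that is less fixed than before. No clinical rule needs to change.

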#### 9 HUMAN SUBJECTS PROTECTIONS

#### 9.1 RATIONALE FOR SUBJECT SELECTION

Since this protocol is a natural history study of patients with VHL and pancreatic lesions, subjects will be selected for this protocol based on either a clinical diagnosis of VHL or a confirmed VHL germ line mutation and an associated pancreatic manifestation as previously described. Patient selection for this protocol will not be based on gender, race, ethnic background or other VHL manifestations.

#### 9.2 Participation of Children

Patients over the age of 12 will be eligible for this study. Since it is unusual for patients under the age of 12 who have pancreatic manifestations, younger patients will not be enrolled. The investigators have experience working with young adolescents and their

Version Date: 08/23/2017

parents in prior protocols. During adolescent participation, the services of the pediatric Clinical Nurse Specialist will be consulted to assist caregivers in addressing the adolescents' developmental needs.

#### 9.3 PARTICIPATION OF SUBJECTS UNABLE TO GIVE CONSENT

Adults unable to give consent are excluded from enrolling in the protocol. However, reconsent may be necessary and there is a possibility, though unlikely, that subjects could become decisionally impaired. For this reason and because there is a prospect of direct benefit from research participation (section 9.4), all subjects ≥ 18 years old will be offered the opportunity to fill in their wishes for research and care, and assign a substitute decision maker on the "NIH Advance Directive for Health Care and Medical Research Participation" form so that another person can make decisions about their medical care in the event that they become incapacitated or cognitively impaired during the course of the study. Note: The PI or AI will contact the NIH Ability to Consent Assessment Team for evaluation. For those subjects that become incapacitated and do not have pre-determined substitute decision maker, the procedures described in NIHMEC Policy 87-4 for appointing a surrogate decision maker for adult subjects who are (a) decisionally impaired, and (b) who do not have a legal guardian or durable power of attorney, will be followed.

#### 9.4 EVALUATION OF BENEFITS AND RISKS DISCOMFORTS

There is the potential for direct benefit for patients participating in this study by early detection of solid lesions of the pancreas associated with VHL and early management of these lesions, which may have an impact on the overall course of the disease. The risks associated with this study with respect to the serial imaging will be minimal. Risks associated with the surgical procedures to manage lesions in the pancreas will vary based on the type lesion and the planned surgical procedure. These risks will be discussed in depth on a patient-by-patient basis. The risks associated with germ line analysis and the potential impact of this genetic information will be discussed with patients through genetic counseling at their initial on-study visit as well as at any subsequent deemed appropriate.

#### 9.5 RISKS/BENEFITS ANALYSIS

For patients who have solid tumors that are not currently amenable to surgical resection, the risk of blood drawing and non-invasive imaging is minor. This study also offers the benefit of surgery, when patients meet the criteria for resection, in an institution with vast experience with the patient with VHL. For pediatric patients, this protocol falls in pediatric risk category 2 because it has more than minimal risk but possible direct benefit.

## 9.6 CONSENT AND ASSENT PROCESS AND DOCUMENTATION

All patients and/or the patient's parent(s) or legal guardian (if he/she is <18 years of age) who are being considered for this trial will undergo informed consent prior to being enrolled on the trial. The PI or one of his designees will perform the consenting process. Patients will be asked to read the consent and will be encouraged to ask questions. It will be stated clearly that participation in the research study is voluntary and that participants can withdraw from the study without losing benefits they would otherwise be entitled to.

Version Date: 08/23/2017

Patients will be enrolled after the consent document has been signed. Separate consents will be obtained for any surgical procedures performed.

#### 9.6.1 Consent of Children

The investigators are requesting a waiver from the IRB to allow only one parent to sign the informed consent to enter a child on the protocol. Because many patients must travel to the NIH from long distances at substantial expense, requiring both parents to be present for the consent process could be a financial hardship for many families. When guardianship status of the child is uncertain, documentation of custody status must be obtained.

#### 9.6.1.1 Consent of Children when there is Joint Custody

In situations where there is joint custody of a child, both parents must sign consent. If only one parent can be present at NIH, the other parent's consent can be obtained by telephone via the procedure described in section 9.6.3.

#### 9.6.1.2 Verbal Consent of Children

Where deemed appropriate by the clinician and the child's parent(s) or guardian, the child will also be included in all discussions about the trial and age-appropriate language will be used to describe the procedures and tests involved in this study, along with the risks, discomforts and benefits of participation. Written assent will not be obtained from children as the study holds out the prospect of direct benefit that is important to the health and well-being of the child and is available only in the context of the research. Verbal assent will be obtained and the parent or guardian will sign the designated line on the informed consent attesting to the fact that the child has given assent. The consent/assent process will be documented in the child's medical record, including the assessment of the child's ability to provide assent (verbal versus written) as applicable. All children will be contacted after they have reached the age of 18 to determine whether they wish to continue on the trial and informed consent will be obtained from them at that time.

## 9.6.2 Consent for minors when they reach the age of majority

When a pediatric subject reaches age 18, continued participation will require consenting of the now adult with the standard protocol consent document to ensure legally effective informed consent has been obtained. Given the length of time that may have transpired for some of the subjects since their last visit for this study, we request waiver of informed consent for those individuals who have completed their participation in the research study.

Requirements for Waiver of Consent consistent with 45 CFR 46.116 (d):

- (1) The research involves no more than minimal risk to the subjects.
  - a. Analysis of samples and data from this study involves no additional risks to subjects.
- (2) The waiver or alteration will not adversely affect the rights and welfare of the subjects.
  - a. Retention of these samples or data does not affect the welfare of subjects.

Version Date: 08/23/2017

(3) The research could not practicably be carried out without the waiver or alteration.

- a. Considering the length of time between a minor's enrollment and their age of majority, it is possible that more than a few subjects may be lost to follow up. A significant reduction in the number of samples analyzed could impact the quality of the research.
- (4) Whenever appropriate, the subjects will be provided with additional pertinent information after participation.
  - a. We only plan to request a waiver of reconsent for those subjects who have been lost to follow-up or who, prior to the approval of Amendment N, have been taken off study prior to reaching the age of majority.

#### 9.6.3 Telephone Re-Consent Procedure

The informed consent document will be sent to the subject. An explanation of the study will be provided over the telephone after the subject has had the opportunity to read the consent form. The subject will sign and date the informed consent. A witness to the subject's signature will sign and date the consent.

The original informed consent document will be sent back to the consenting investigator who will sign and date the consent form with the date the consent was obtained via telephone.

A fully executed copy will be returned via mail for the subject's records.

The informed consent process will be documented on a progress note by the consenting investigator and a copy of the informed consent document and note will be kept in the subject's research record.

#### 9.6.4 Informed consent of non-English Speaking Subjects

We anticipate the enrollment of Spanish speaking research participants into our study. The IRB approved full consent document will be translated into that language in accordance with the Clinical MAS Policy M77-2.

If there is an unexpected enrollment of a research participant for whom there is no translated extant IRB approved consent document, the principal investigator and/or those authorized to obtain informed consent will use the Short Form Oral Consent Process as described in MAS Policy M77-2, OHSRP SOP 12, and 45 CFR 46.117 (b) (2). The summary that will be used is the English version of the extant IRB approved consent document. Signed copies of both the English version of the consent and the translated short form will be given to the subject or their legally authorized representative and the signed original will be filed in the medical record.

Unless the PI is fluent in the prospective subject's language, an interpreter will be present to facilitate the conversation (using either the long translated form or the short form). Preferably someone who is independent of the subject (i.e., not a family member) will assist in presenting information and obtaining consent. Whenever possible, interpreters will

Version Date: 08/23/2017

be provided copies of the relevant consent documents well before the consent conversation with the subject (24 to 48 hours if possible).

We request prospective IRB approval of the use of the short form process for non-English speaking subjects and will notify the IRB at the time of continuing review of the frequency of the use of the Short Form.

Version Date: 08/23/2017

